#### Randomization Schedule

Vaccination Group	Stratification		
	STM	HM ‡	Total
V212	1348	1284	2632
Placebo	1348	1284	2632
Total	2696	2568	5264

‡ HM population will be further stratified into one of two strata, low IC or moderate to high IC which is expected to be in 1:3 ratio approximately.

An Interactive Voice Response System (IVRS) will be used to register patient visits upon randomization and at subsequent visits. The IVRS will be used to allocate patients to vaccination group assignments during randomization according to a central randomization schedule generated by the SPONSOR. For all sites, all vaccine doses will be shipped through the IVRS.

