In a recent Merck-sponsored observational cohort study conducted at KPNC, a US managed care organization, in cancer patients with STM or HM diagnosed between 2001 and 2005, among ~2700 HM patients, the estimated incidence of HZ was 31 per 1000 person-years [13]. In this population, both the underlying cancer diagnosis and the treatment regimen resulted in immunosuppression. In this study, a consensus algorithm developed for database studies by immunology and infectious disease experts was used to classify the level of immunocompromise (IC) of patients into none/low, medium, or high. IC classification, updated on a monthly basis throughout the study period for each patient, was based on (1) the type of chemotherapy agents and/or corticosteroids used, (2) time since last chemotherapy/corticosteroid treatment, and (3) specific type of HM [31]. Corticosteroid therapy was classified into levels of IC based on dose and duration of treatment. Among HM patients, the incidences of HZ were 13, 25, and 48 per 1000 person-years in the low, moderate, and high IC groups respectively. The incidence of HZ was higher for patients who were receiving chemotherapy or corticosteroids during the study period (47 per 1000 person-years) than those who were not (17 per 1000 person-years). The incidences of HZ among patients with multiple myeloma, Hodgkin's lymphoma, non-Hodgkin lymphoma, and myeloid leukemia were 56, 51, 25, and 23 per 1000 person-years respectively. HZ can also be a significant source of morbidity in HM patients. The proportion of HZ cases complicated by PHN and disseminated zoster was estimated to range from ~5% to 33% and 5% to 19%, respectively [22-24, 28-29, 32-33]. In the KPNC study, among 140 incident HZ cases in the HM patients, approximately one in three patients (33.6%) developed at least one complication. PHN (zoster-associated pain persisting or appearing at or beyond 90 days post-HZ onset) occurred in 5.7% HZ cases. The proportion of cases with multiple dermatome involvement, skin-related, eye-related, or neurological complications was 7.9%, 19.3%, 3.6%, and 2.9% respectively.

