### **3.2.12 Stratification/Randomization/Allocation**

Randomization will be stratified by patient population (STM or HM) with approximately 2696 patients with STM and 2568 patients with HM enrolled into the study. Patients with HM will be further stratified into one of two strata (low IC; moderate to high IC), based on the patient's specific HM diagnosis (underlying cancer diagnosis) and/or chemotherapeutic regimen (see Appendix 6.1). The planned randomization schedule by vaccination group is shown in Section 2.4.2.

An IVRS will be used to register patient visits at the time of randomization and at subsequent visits. The IVRS will be used to allocate the patient to the vaccination group assignment and to assign either V212 or placebo to the patient during randomization, according to a centralized randomization schedule generated by the SPONSOR. Study site personnel accessing the IVRS will be assigned an individual unique personal identification number (PIN). Site personnel must use only their specific assigned PIN to access the IVRS and must not share their assigned PIN with anyone.

A separate allocation schedule will be used to allocate those patients participating in the ELISPOT substudy to assure a well-balanced randomization ratio. All investigative sites participating in the immunogenicity substudy will enroll each consented substudy patient until the target enrollment of 1000 patients has been met.

At Visit 1, after the patient has signed the consent form, the medical history has been collected, all inclusion/exclusion criteria are met, a negative serum or urine pregnancy test (sensitive to 25IU  $\beta$ -hCG) has been obtained, and the prevaccination blood sample has been collected (if applicable), site personnel will access the IVRS using their PIN. The IVRS will assign an allocation number to the patient, followed by the assignment of unique component identification number (CID) corresponding to the vial of vaccine/placebo and diluent the patient should receive at that visit. The CID on the vaccine/placebo vial and the CID on the diluent vial will be unique. The IVRS will automatically assign the appropriate clinical material based on the patient's treatment allocation.

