### 3.5.5.1.2 Analysis of Vaccine Efficacy on Secondary Efficacy Endpoints

Three secondary efficacy endpoints are defined for the STM population and in the HM population on an exploratory basis.

Since the incidences of moderate to severe HZ-associated pain, HZ-complications as defined by the composite endpoint, and PHN are unknown in this population, formal hypothesis testing for these secondary endpoints will not be performed. The incidence of the secondary efficacy endpoints of moderate to severe HZ-associated pain, composite complication endpoint, and the incidence of PHN, defined as pain in the area of the HZ rash with a “worst pain in the last 24 hours” score of 3 or greater (on a 0 to 10 scale) on the ZBPI that persists or appears greater than or equal to 90 days after HZ onset, (point estimate and 95% CI) will be compared between vaccine and placebo groups using Cox proportional hazards regression stratified by age (< 50 years of age versus  $\geq$  50 years of age) based on the MITT population. For patients who develop PHN, the PHN event onset will be the date of HZ rash onset. Patients who do not develop PHN will be considered as censored at the stop date of their HZ surveillance. Furthermore, the count and proportion of each component of the secondary efficacy composite endpoint among all randomized patients in the vaccine and placebo groups will be summarized.

Sensitivity analyses for vaccine efficacy on PHN based on alternative definitions [pain in the area of the HZ rash with a “worst pain in the last 24 hours” score of 3 or greater (on a 0 to 10 scale) on the ZBPI that persists or appears more than 30, 60, 120, and 180 days after HZ rash onset] will be compared between the vaccine and placebo groups in the MITT population.

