For Tier-1 adverse experiences, risk differences between the two groups, corresponding two-sided 95% CI on the risk difference, and the p-value for the test of significant risk difference will be provided. The corresponding p-value will be based on the normal approximation for testing two independent binomial proportions at the two-sided 0.05 level adjusting for stratification factors. The risk difference and 95% CI will be calculated using the methods proposed by Miettinen and Nurminen [20]. Tier 1 adverse experiences include (1) systemic adverse experiences prompted for on the VRC, including varicella/varicella-like or an HZ/HZ-like rash occurring after any study vaccination through 28 days Postdose 4, (2) injection-site complaints prompted for on the VRC, such as redness, swelling, and pain/tenderness/soreness occurring Day 1 through Day 5 after any vaccination, and (3) elevated temperature ( $\geq 100.4^{\circ}\text{F}$  [ $\geq 38.0^{\circ}\text{C}$ ]), after any study vaccination through 28 days Postdose 4.

Additional summaries on Tier-1 safety parameters will also be provided by the dosing period..

For Tier-2 adverse experiences, risk differences between the two groups and the corresponding two-sided 95% CI on the risk difference will be provided using the methods proposed by Miettinen and Nurminen. This Tier-2 approach will be applied to the proportions of any other injection-site adverse experiences or systemic adverse experiences after any study vaccination through 28 days Postdose 4 that are not prompted for on the VRC but occurred in at least 1% of the patients in either treatment group.

Additional summaries on Tier-2 safety parameters will also be provided by the dosing period, and gender in each vaccination group.

Tier 3 adverse experiences will include summaries for any other adverse experiences after any study vaccination through 28 days Postdose 4.

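### The age-stratified Cox model for the three secondary endpoints omits, for HM, the immunocompromise stratum used in HM randomization; adding it is a free improvement with a very small effect

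*Combined protocol and SAP*

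**What the plan says.** Randomization. Section 3.2.12 states: "Patients with HM will be further stratified into one of two strata (low IC; moderate to high IC"), according to diagnosis and/or chemotherapy regimen. The note to Table 2-1 describes the two strata as "low IC or moderate to high IC which is expected to be in 1:3 ratio approximately". Age is not named as a randomization factor in 2.4.1, 2.4.2 or 3.2.12.

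Secondary endpoints. Section 3.5.5.1.2 opens: "Three secondary efficacy endpoints are defined for the STM population and in the HM population on an exploratory basis". It then gives one model for all three, "using Cox proportional hazards regression stratified by age" (under 50 versus 50 and over), in the MITT population. It plans no formal testing of these endpoints.

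Other efficacy analyses. The Cox model in 3.5.5.1.1 is defined for STM. For HM HZ incidence, Table 3-2 lists summaries only, although the impact of V212 on HZ in HM is exploratory objective 2 in 2.1.4. The log-rank comparison is unadjusted. The ANCOVA models in 3.5.5.1.3 take covariates like those of the primary analysis, which names only age. IC category enters the efficacy plan once, in 3.5.5.1.5, as a subgroup for summaries.

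Safety. Section 3.5.5.3 analyses HM and STM separately and bases the Tier-1 p-values on a test "adjusting for stratification factors".

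**The concern.** A factor used to stratify randomization is normally carried into the analysis, above all when it predicts the outcome. Here the model uses age, which was not a randomization factor, and for HM leaves out IC, which was. The age-only model suits STM, which has no IC strata, but the same sentence serves for HM.

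Two consequences follow. In a Cox model, leaving out a prognostic factor pulls the hazard ratio towards 1, even when the arms are balanced on it, so HM efficacy would be slightly understated. And within the same HM population, the safety tests would use the randomization strata while the efficacy models would not, with no reason given. At stake are consistency with the design and a model for HM that is fixed before final unblinding.

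**Working it through.** **The plan's own figures.** The plan gives no figure for the HM efficacy models. Its main design figure, 84.2% power with 90 STM cases, is not affected. It reproduces from the exact binomial split of cases: vaccine share 0.75/1.75 under the null and 0.35/1.35 at VE 65%, success with 27 or fewer of 90 cases in the vaccine group, power 84.2%. IC strata do not exist in STM.

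**Inputs from the documents**
- HM sample: 2568, so 1284 per arm (3.2.12, Table 2-1).
- IC split: 1:3, so weights 0.25 (low) and 0.75 (moderate to high).
- Prognostic strength, from 3.1.1.1: "the incidences of HZ were 13, 25, and 48 per 1000 person-years in the low, moderate, and high IC groups respectively". Relative to low IC, that is 25/13 = 1.9-fold and 48/13 = 3.7-fold.

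**Assumptions.** VE is equal in both IC strata; follow-up is uniform over 2 to 5 years; there is no dropout. The moderate-to-high stratum pools two levels, so its rate is varied from 25 to 48, the upper end being extreme.

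**Step 1: the mechanism by hand.** Take true HR 0.50 and rates 13 and 48. The average hazard among those still event-free at time t, with arm multiplier θ (1 for placebo, 0.5 for vaccine), is

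Σ wᵢ rᵢθ exp(−rᵢθt) / Σ wᵢ exp(−rᵢθt).

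- At t = 0: placebo 0.25×13 + 0.75×48 = 39.25; vaccine 19.625; ratio 0.500.
- At t = 3.5 years, the placebo weights become 0.25e^(−0.0455) = 0.2389 and 0.75e^(−0.168) = 0.6340. The hazard is (0.2389×13 + 0.6340×48)/0.8729 = 38.42.
- At t = 3.5 years, the vaccine weights become 0.25e^(−0.02275) = 0.2444 and 0.75e^(−0.084) = 0.6896. The hazard is (0.2444×6.5 + 0.6896×24)/0.9340 = 19.42.
- The ratio at 3.5 years is 19.42/38.42 = 0.5055.

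The ratio drifts towards 1, but slowly, because few patients have events.

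**Step 2: large-sample value of the Cox estimate without IC.** Let R₀ and R₁ be the expected risk sets and f₀ and f₁ the event densities by arm. The limit b solves ∫[f₁ − (f₀+f₁)R₁eᵇ/(R₀+R₁eᵇ)]dt = 0.

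| True VE | VE without IC, rates 13 and 25 | VE without IC, rates 13 and 48 |
|---|---|---|
| 65% | 64.95% | 64.75% |
| 50% | 49.94% | 49.72% |
| 25% | 24.96% | 24.79% |

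The largest shift is 50 − 49.72 = 0.28 points.

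**Step 3: simulation** (1284 per arm, IC balanced 1:3, Efron ties, 200 runs, true VE 50%).

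| Rates | VE without IC (SE of log HR) | VE with IC (SE of log HR) |
|---|---|---|
| 13 and 48 | 49.2% (0.134) | 49.5% (0.134) |
| 13 and 25 | 50.2% (0.178) | 50.3% (0.178) |

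A separate run of 300 trials (true VE 30%, rates 13 and 48, mean follow-up 2.5 years) gave mean log HR −0.370 without IC and −0.373 with it, SE 0.143 in both. On the VE scale that is 1 − e^(−0.370) = 30.9% against 1 − e^(−0.373) = 31.1%, a difference of 0.2 points.

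All of these use HZ incidence rates. The documents give no rates by IC level for pain, complications or PHN, so the three endpoints themselves were not simulated.

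**The case against.** The strongest reply is that this changes nothing that matters. HM was stopped for futility, its efficacy objectives are exploratory, the endpoints are estimated and not tested, and 3.5.5.1.5 already summarizes HZ, the complications composite and PHN by HM IC category. All of that stands, and it is why the point is a free improvement and no more.

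A reader might infer that every HM efficacy model is age-only, HZ incidence included. The documents do not support that. The model in 3.5.5.1.1 is written for STM, and Table 3-2 gives only summaries for HM HZ incidence, so a Cox model there is unspecified. Even for the secondary endpoints, 2.7.1 ties the age-stratified model to STM; its use in HM rests on 3.5.5.1.2, where it is the natural reading.

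A reader might also expect the change to remove chance imbalance in IC. It would add little, because randomization already balances IC.

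Nor is the safety plan in contradiction with the efficacy plan. Risk differences and hazard ratios may be adjusted differently. The contrast shows only an unexplained inconsistency.

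Finally, PHN will be sparse. At 5.7% of HM HZ cases (3.1.1.1), the 68-case interim threshold gives 68×0.057 = 3.9 events, and twice that number of cases gives 136×0.057 = 7.8, spread over four age-by-IC strata. The estimate will be imprecise either way. Finer strata should cost little, since each event is compared with a risk set that randomization keeps near 1:1; the low-IC stratum alone would hold about 2568/4 = 642 patients before the age split. That is an argument and was not simulated; a very small age-by-IC cell could be an exception.

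**Conclusion.** The point holds for the three secondary-endpoint Cox models as applied to HM: they omit the stratum by which those patients were randomized, and that stratum is prognostic for HZ in the protocol's own data. The size is very small. With the HZ rates by IC level, VE shifts towards zero by about 0.3 percentage points or less, with no visible change in the standard error. This rests on a common VE across IC strata, follow-up of 2 to 5 years without dropout, and HZ rates standing in for the secondary endpoints. HM close-out began in November 2014, so actual follow-up is probably shorter and the shift in HZ smaller still.

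It should not be read as a material bias in the HM results, as a reason to doubt the futility decision, or as touching the STM primary analysis. The documents support none of these. The case is consistency with the design at almost no cost.

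**What to change.** In 3.5.5.1.2, add that for HM the Cox models for pain, complications and PHN are stratified by IC category (low; moderate to high) in addition to age, and that any Cox model fitted for HM HZ incidence under exploratory objective 2 uses the same strata. Leave the STM primary model in 3.5.5.1.1 unchanged.

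The cost is one sentence. The IC stratum is in the randomization data and is already used in 3.5.5.1.5. Because these HM analyses are exploratory, section 3.5 allows the change to be recorded in the Clinical Study Report with its timing and reason, without an amendment. It is best fixed before final unblinding, so that the model is not chosen after the results are seen.

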### **3.5.5.1.3 Analysis of Vaccine Efficacy on Exploratory Endpoints**

The following exploratory efficacy analyses will be conducted for the STM and HM populations separately.

To evaluate the vaccine effect on the severity of HZ pain among HZ cases, the severity-by-duration of HZ pain (calculated as the area under the “worst pain in the last 24 hours” versus time curve) will be summarized by vaccination group on a MITT population. To compare the mean severity-by-duration measure of HZ pain among patients who develop HZ between the two vaccination groups, an analysis of covariance (ANCOVA) model adjusting for similar covariates as for the primary efficacy analysis will be used to get the point estimate and a bootstrap method will be used to obtain 95% CI of HZ severity-by-duration scores difference between the vaccination groups. Additional exploratory analysis may include the use of antiviral drug initiated within 72 hours of HZ rash onset (Yes versus No) as an additional covariate.

In addition, the mean and median duration of HZ pain (time from rash onset to the first visit when pain score became persistently < 3) will be provided by vaccination group. The mean HZ pain score, the numbers of lesions, dermatomes and extent of rash (defined as the maximum area of the HZ rash at each HZ follow-up visit), the mean ADLI score and the mean EuroQoL score will be summarized by vaccination group. ANCOVA models will also be used to compare these mean scores between the two vaccination groups at each HZ follow-up visit. In addition, the score-by-duration of ADLI and score-by-duration of general health status score in EuroQoL over 6 months post-HZ onset (calculated by area under the ADLI curve and general health status score curve, respectively) will be summarized by vaccination group and compared by ANCOVA model.

Poisson regression with generalized estimating equations will be used to evaluate the effect of the vaccine on the rates of non-protocol mandated health care utilization and work loss. If the counts of health care contacts in each treatment group are less than 10, then an exact binomial method will be used to calculate the CIs rather than generalized estimating equations.

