#### **2.1.4 Exploratory Objectives**

1. To assess the safety and tolerability of V212 when administered to adults with HM.
2. To assess the impact of V212 on the development of HZ in adults with HM.
3. To assess the impact of V212 on the development of moderate to severe HZ-associated pain at any time from HZ onset through the end of the 6 month HZ follow-up period. Moderate to severe HZ-associated pain is defined as 2 or more occurrences of a score of 3 or greater (0-to-10 scale) on the Zoster Brief Pain Inventory (ZBPI) in adults with HM.

4. To assess the impact of V212 on the development of HZ complications defined as the occurrence of any of the following during the study: hospitalization or prolongation of hospitalization due to HZ, disseminated HZ (including disseminated HZ rash or VZV viremia), visceral HZ, ophthalmic HZ, neurological impairment due to HZ, or administration of intravenous acyclovir therapy for treatment of HZ in adults with HM.
5. To assess the impact of V212 on the development of PHN. PHN is defined as a worst pain score (in the previous 24 hours) of 3 or greater (0-to-10 scale) on the ZBPI, that persists or appears greater than or equal to 90 days after the onset of HZ rash in adults with HM.
6. To assess the immunogenicity of V212 in adults with STM or HM.
7. To describe the impact of HZ on activities of daily living (ADL) and quality of life (QoL), and to assess the impact of V212 on interference with ADL and QoL in study patients who develop HZ.
8. To describe HZ-related non-protocol-mandated health care resource utilization (HCRU), and assess the impact of V212 on HZ-related non-protocol-mandated HCRU, and work and productivity loss (WPQ).
9. To assess the impact of V212 on the severity and duration of HZ-related pain.
10. To assess the impact of V212 on the severity of HZ rash including the extent of rash, number of skin lesions present, and number of dermatomes involved.
11. To assess the association of immunogenicity at postvaccination with the risk of HZ in adults with STM or HM.

The exploratory objectives (1)-(5) will be evaluated for HM only; objectives(6)-(10) will be evaluated for STM and HM separately and (11) will be evaluated in both combined STM and HM populations and individual subpopulation.

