- The severity-by-duration of HZ pain (defined as the average area under the “worst pain in the last 24 hours” versus time curve) from the first day of HZ onset through 6 months after HZ onset.
- The duration of pain (defined as number of days from rash onset to the first visit when pain score on the ZBPI became persistently < 3).
- The numbers of lesions, number of dermatomes and extent of rash (defined as the maximum area of the HZ rash at each HZ follow-up visit).
- The impact of HZ on ADL, as measured by the score-by-duration of activity-of-daily-interference (ADLI) (defined as the average area under ADLI versus time curve) from the first day of HZ onset through 6 months after HZ onset. ADLI is a single combined score calculated by averaging 7 separate items (regarding general activity, mood, walking ability, normal work, relations with others, sleep, and enjoyment of life) collected in the ZBPI at each HZ follow-up visit.
- The impact of HZ on general health status, as measured by the score-by-duration in the EuroQoL from the first day of HZ onset through 6 months after HZ.
- HZ-related non-protocol-mandated HCU and work and productivity loss. The analyses will be covered in a separate internal SAP, prepared by the Health Economist of the study.

Of note, the exploratory efficacy analyses will be evaluated for the HM and STM populations separately.

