### **3.5.4 Analysis Populations**

#### **3.5.4.1 Efficacy Analysis Populations**

##### **Modified Intent-To-Treat (MITT) Population**

The key summaries and analyses for the primary, secondary and exploratory efficacy endpoints will be based on the MITT population (see Table 3-2). This population will include all randomized patients who received at least one dose of the vaccination. Those randomized patients who are excluded from the MITT population will be listed. The efficacy analyses will be performed based on the treatment group to which those subjects are randomized.

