To evaluate the vaccine effect on PHN above and beyond that on HZ incidence, the proportions of patients who develop PHN among HZ cases will be provided by vaccination group. A generalized linear regression model with log-link will be used to estimate the relative risk reduction of PHN among HZ cases in vaccine recipients compared with placebo recipients. This model will include incidence of PHN as a binary response variable, and include vaccination group, and age as covariates. An exploratory analysis will be performed using the similar model, with the use of antiviral drug initiated within 72 hours of HZ rash onset (Yes versus No) added as an additional covariate. Note that these analyses are not protected by randomization, and with the post-randomization variable, antiviral use in the model, the results might be subject to potential bias.

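### The continuous pain score is compared between groups only among patients who develop HZ, a set the vaccine helps select; separately, the score is defined in two ways

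*Combined protocol and SAP*

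**What the plan says.** **Objectives (section 2.1.4).** Objective 9 is unconditional: "To assess the impact of V212 on the severity and duration of HZ-related pain". Objective 7 is not; for daily living and quality of life it asks "to assess the impact of V212 on interference with ADL and QoL in study patients who develop HZ".

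**Population.** Section 3.5.4.1 states: "The key summaries and analyses for the primary, secondary and exploratory efficacy endpoints will be based on the MITT population". Table 3-2 also lists the exploratory scores under MITT. Section 3.5.5.1.3 says the pain score "will be summarized by vaccination group on a MITT population", and its next sentence narrows the comparison: "To compare the mean severity-by-duration measure of HZ pain among patients who develop HZ between the two vaccination groups". No value is given for a patient who never has HZ.

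**Method.** The comparison is an ANCOVA with covariates like those of the primary analysis, which is stratified by age only. A bootstrap supplies the 95% CI, and early antiviral use may be added as a covariate. Duration of pain is only summarised.

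**Caveat.** Section 3.5.5.1.2 plans a parallel analysis of PHN among HZ cases and warns: "Note that these analyses are not protected by randomization". Section 3.5.5.1.3 has no such warning.

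**Score.** Section 3.5.3.1 has the pain score "defined as the average area under the" worst-pain curve, from HZ onset through 6 months. Section 3.5.5.1.3 has it "calculated as the area under the" same curve. The daily-living interference score (ADLI) shows the same mismatch.

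**Other pain analyses.** Section 3.5.5.1.2 compares moderate-to-severe HZ pain and PHN by Cox model in the whole MITT population.

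**The concern.** Randomisation balances the two arms at entry. It does not balance the patients who later develop HZ, because the vaccine affects who they are. If it prevents some kinds of case more readily than others, the remaining vaccine cases differ in kind from the placebo cases, and a difference in mean pain then mixes that selection with any real effect on pain. Adjusting for age does not remove this.

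At stake is how objective 9 will be read. Section 3.1.2.3 expects the exploratory outcomes to add confirmation of a clinically meaningful effect on HZ disease. A case-only mean can move against the effect on total pain, or can flatter it, and the table would carry no warning.

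The second matter is independent of the first. With two wordings of the score and no rule for curves cut short, two programmers could produce different values for the same patient.

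**Working it through.** **Step 1: expected case split.** Inputs from section 3.5.7.1: 90 STM cases, 1:1 allocation (1348 per arm), VE 65%, null VE 25%, two-sided 0.025. Given 90 cases, the vaccine share is 0.75/1.75 = 0.4286 under the null and 0.35/1.35 = 0.2593 at VE 65%. An exact binomial test at one-sided 0.0125 succeeds with at most 27 vaccine cases, and its power is 84.2%. This matches the plan, and the other five entries of Table 3-3 also reproduce. The expected split is 90 × 0.2593 = 23.3 vaccine and 66.7 placebo cases.

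**Step 2: what the case-only mean does.** The documents give no mean or SD for the score, so these are assumptions: area 100 for a mild case, 600 for a severe one, and a share s of placebo cases severe. For s I use 0.2 and 0.4, two of the shares that section 3.5.7.1 uses for secondary outcomes. Overall VE is held at 65%, so VE(severe) = [0.65 − (1 − s) × VE(mild)] / s.

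Worked case, s = 0.4 and VE(mild) = 75%:
- VE(severe) = (0.65 − 0.45)/0.4 = 50%.
- Placebo mean = 0.6 × 100 + 0.4 × 600 = 300.
- Vaccine cases: mild 66.7 × 0.6 × 0.25 = 10.0; severe 66.7 × 0.4 × 0.50 = 13.3.
- Vaccine mean = (10.0 × 100 + 13.3 × 600)/23.3 = 386, which is 29% higher.
- Burden per MITT patient, zero for non-cases: 66.7 × 300/1348 = 14.84 on placebo and 23.3 × 386/1348 = 6.68 on vaccine, which is 55% lower.

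| s | VE mild / severe | Cut in breakthrough pain | Case-only mean, V vs P | Case-only difference | MITT burden |
|---|---|---|---|---|---|
| 0.4 | 65% / 65% | none | 300 vs 300 | 0% | −65% |
| 0.4 | 75% / 50% | none | 386 vs 300 | +29% | −55% |
| 0.4 | 75% / 50% | 30% | 270 vs 300 | −10% | −68% |
| 0.4 | 55% / 80% | none | 214 vs 300 | −29% | −75% |
| 0.2 | 75% / 25% | none | 314 vs 200 | +57% | −45% |
| 0.2 | 75% / 25% | 30% | 220 vs 200 | +10% | −61% |

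In the second, fourth and fifth rows the vaccine changes no breakthrough case's pain, yet the case-only difference runs from −29% to +57%. With VE 75% against mild cases, the cut in breakthrough pain that brings the difference to zero is 1 − 300/386 = 22% for s = 0.4 and 1 − 200/314 = 36% for s = 0.2.

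**Step 3: the two definitions.** If the average divides by the fixed 6-month window, it is the area times a constant, and ratios and tests are unchanged. If it divides by days observed, the scores part when follow-up is cut short. Pain of 6 for 30 days has area 6 × 30 = 180. That averages 180/30 = 6.0 if the patient dies on day 30, and 180/182 = 1.0 if the patient is pain-free to day 182. The documents do not say which divisor is meant.

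**The case against.** Much can be said for the plan.

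- **The case-only question is stated openly.** Section 3.5.5.1.3 introduces the pain analysis as one among HZ cases, and objective 7 restricts the daily-living and quality-of-life effect to patients with HZ. This stands for objective 7. It does not settle objective 9, which has no such limit.
- **Pain is compared in MITT elsewhere.** A reader might infer that the plan never compares pain over the randomised population. Section 3.5.5.1.2 shows otherwise: moderate-to-severe pain and PHN, including the PHN sensitivity cut-offs, are compared in MITT and rank higher. This stands and narrows the point to the continuous score.
- **The direction is not known.** A reader might infer that the vaccine would appear to worsen pain. That needs better protection against mild cases and too little attenuation of breakthrough cases to offset it. The documents do not show that pattern. Section 3.1.2.2 reports, in transplant recipients, that a 3-dose regimen lowered HZ severity without changing incidence. This stands: the bias has no known sign.
- **The MITT label may simply mean HZ cases drawn from MITT.** Section 3.5.4.1 describes a comparable HZ subset of the per-protocol population. That is a fair reading, but the text should say so.
- **The score mismatch may only rescale.** A reader might infer a six-fold distortion, or that the mismatch drives an apparent worsening. The six-fold figure is one hypothetical patient under one reading of the average, and the wording has no part in the selection effect.
- **An MITT score has its own faults.** It mixes incidence with severity, and early deaths or losses would score as pain-free unless follow-up is handled.

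These endpoints are exploratory and without multiplicity control, so no confirmatory claim is affected.

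**Conclusion.** The point holds in limited form. The only between-group comparison of the severity-by-duration pain score conditions on developing HZ, adjusts for age, and lacks the caveat that the plan gives its parallel PHN analysis. It therefore does not give a randomised answer to objective 9.

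Under the assumed areas, with about 67 placebo and 23 vaccine cases, the case-only difference is zero when VE does not depend on severity. Otherwise it ranges in the scenarios shown from 29% lower to 57% higher, while MITT burden falls 45% to 75%. These figures show that size and sign are not assured; they do not predict this trial. They rest on the 100 and 600 areas, the severe shares, and overall VE of 65%.

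The two wordings of the score are a separate inconsistency to be reconciled. Its effect on the group contrast cannot be sized from the documents. The primary and secondary analyses are untouched.

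**What to change.** 1. In section 3.5.5.1.3, add an MITT pain-burden comparison: area under the worst-pain curve from HZ onset to 6 months, zero for patients without confirmed HZ, and a difference or ratio of means with a bootstrap CI, the method already planned for the pain score.
2. State how unequal or truncated HZ surveillance is handled, for example by burden per person-year, and how a pain curve cut short by death or loss is completed. Section 3.5.7.1 assumes 30% loss to follow-up, so a plain zero for early leavers is not enough.
3. Optionally do the same for ADLI. Do not extend it to EuroQoL: the section 1.8 flow chart schedules it only for suspected HZ, and a health-status score has no neutral zero.
4. Keep the HZ-only ANCOVA as descriptive, name its population as HZ cases within MITT, and carry over the section 3.5.5.1.2 caveat on randomisation and on antiviral use as a covariate.
5. Use one definition in sections 3.5.3.1 and 3.5.5.1.3 for pain and ADLI: area over the fixed 6-month window.

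The cost is one further analysis on data already collected, plus wording. Because the MITT score mixes incidence and severity, the HZ-only table should stay beside it.
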